Title:

Effect of Pomegranate Seed Powder on
markers of Metabolic Syndrome

NCT:

Not Assigned yet

Submission Date:

Uploaded here on 21st June, 2023

STATEMENT OF PROBLEM

A number of chronic disorders can lead to metabolic syndrome, which has been identified as one of the key risk factors for the epidemic of type 2 diabetes and cardiovascular diseases in the twenty-first century. Thus, it's a high time to mitigate the prevalence of these risk factors to overcome metabolic syndrome.

Objective:

To evaluate the effectiveness of pomegranate seed powder supplementation in preventing metabolic dysfunction and its main risk factors, such as hypertension and cardiovascular illnesses.

Study Protocol

Type of Study

This trial is prospective clinical type.

Supplement preparation

Pomegranate seeds and arils will be separated, and then the seeds will be dried for 15 days in a lab environment. Later, a mechanical grinder will be used to powder the dried seeds. PS powder (PSP) will be packed in a capsule form, 5 g in each.

Participants

The population under study will be consisted of people suffering with any of the three metabolic impairments; Insulin resistance, obesity, disturbed glucose level, hyper-cholesterol, hypertension and higher blood pressure. Exclusion criteria will be critically ill or hospitalized patients and individuals with digestion and absorption issues.

Span of study

The clinical trial on the 50 patients of metabolic syndrome will be conducted for the duration of 8 weeks with the supplementation of PSP capsule, twice a day.

Outcome Evaluation

Blood pressure, total cholesterol, and triglycerides (TG) will be measured at the enrollment point (i.e., baseline) and at the end of the 8-week intervention period. Fasting blood glucose (FBG), glycated haemoglobin (HbA1c), and triglycerides (TG) will be measured at the enrollment point (i.e., baseline). A fresh blood sample from a vein will then be taken and examined. A calibrated digital weight scale will also be used to check the patient's weight. Detail of all data collected is as follows:

Anthropometric Measurements:

- Weight
- Height
- Skin fold Thickness

Biochemical Evaluation:

- Blood Pressure
- Fasting Blood Glucose
- Total Cholesterol
- Triglycerides

Clinical Evaluation:

- Obesity

Statistical Analysis Plan

Using one-way ANOVA, the statistical significance of the host parameter data will be determined (SPSS Inc., Chicago, IL, USA). When the p-values are less than 0.05, differences are considered significant. Statistical analyses will be carried out in the R programming environment for data sequencing. For both quantitative and qualitative variables, data will be displayed as means \pm SD or frequency (percent), respectively.

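### The objective claims prevention of illness that no planned outcome measures, and effectiveness from a comparison the plan does not define

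*Combined protocol and SAP*

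**What the plan says.** - **Objective:** "To evaluate the effectiveness of pomegranate seed powder supplementation in preventing metabolic dysfunction and its main risk factors, such as hypertension and cardiovascular illnesses".
- **Title:** narrower, an effect on "markers of Metabolic Syndrome".
- **Type of Study**, in full: "This trial is prospective clinical type".
- **Span of study**, on who is treated and for how long: "The clinical trial on the 50 patients of metabolic syndrome will be conducted for the duration of 8 weeks with the supplementation of PSP", taken as a capsule twice daily. No placebo, comparator or untreated group is mentioned in any section.
- **Participants:** "people suffering with any of the three metabolic impairments; Insulin resistance, obesity, disturbed glucose level, hyper-cholesterol, hypertension and higher blood pressure".
- **Outcome Evaluation**, on timing: "Blood pressure, total cholesterol, and triglycerides (TG) will be measured at the enrollment point (i.e., baseline) and at the end of the" …; the second time point is week 8. Fasting blood glucose (FBG) and HbA1c are given a baseline time only. Weight, height, skin fold thickness and obesity are listed with no stated time.
- **Statistical Analysis Plan:** "Using one-way ANOVA, the statistical significance of the host parameter data will be determined", with significance at p below 0.05. The factor that defines the ANOVA groups is not named.

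**The concern.** The objective makes two claims, and each has its own problem.

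The first is prevention. To show that an illness was prevented, a trial needs people who are free of it at entry and an outcome that records whether it occurs. The plan enrols people who already have metabolic syndrome, and it defines no such outcome.

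The second is effectiveness, meaning that PSP caused the change. That needs something to compare PSP with. The plan describes one treatment and no comparison group.

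The only decision rule is p below 0.05. Under the present wording, a significant fall in one marker could be reported as evidence that PSP prevents hypertension or cardiovascular illness. The data described would show at most that a marker changed.

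**Working it through.** The plan gives no power, effect size, SD or allocation, so it contains no derived figure to reproduce. The check is mainly a comparison of its sections, with one illustration.

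**Step 1. Prevention: the objective against entry and outcomes.**

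| Target in the Objective | State at entry | Planned outcome |
|---|---|---|
| Metabolic dysfunction | Already present: all 50 are described as having metabolic syndrome | Marker levels, not onset |
| Hypertension | On the list of entry impairments; some participants may not have it | Blood pressure at baseline and week 8; no threshold, at-risk subset or onset analysis |
| Cardiovascular illness | Not addressed | None recorded |

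No row has both an at-risk group and an onset outcome. Adding a control group would change none of the rows. Recording cardiovascular events would not help much either: 50 patients × 8/52 year = 7.7 person-years, so at assumed annual rates of 1% to 5% the expected count is 0.08 to 0.38 events.

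**Step 2. Effectiveness: what one treated group can show.** With a single group,

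mean change = PSP effect + time trend + diet or treatment change + placebo response + regression to the mean.

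The data give one number, the left-hand side, and nothing in the plan separates the terms on the right. A different before/after test changes the precision of that number but not what it is made of.

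**Step 3. Illustration.** From the plan: n = 50 and the 0.05 threshold (taken as two-sided). Assumed: a mean shift of 0.2 or 0.5 SD unrelated to PSP, and a correlation ρ of 0.6 to 0.9 between visits.

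- *Paired t-test (not named in the plan).* Standardised change = shift / √(2(1−ρ)). For a shift of 0.2 and ρ = 0.7 this is 0.2/√0.6 = 0.258; the noncentrality is 0.258 × √50 = 1.83, and the chance of significance is 43%.
- *One-way ANOVA with the two visits treated as independent groups* (F on 1 and 98 df, simulated). Same inputs: 4.4%. It ignores the pairing, so its error term is too large.
- *Two concurrent groups of 25, both with the 0.2 SD shift,* ρ = 0.7 (simulated): 5.1% on change and 5.0% on week-8 values, which is the nominal rate.

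| Shift | Test | ρ = 0.6 | 0.7 | 0.8 | 0.9 |
|---|---|---|---|---|---|
| 0.2 SD | Paired | 34% | 43% | 59% | 87% |
| 0.2 SD | ANOVA on visits | 6.7% | 4.4% | 2.2% | 0.4% |
| 0.5 SD | Paired | 97% | 99% | 100% | 100% |
| 0.5 SD | ANOVA on visits | 79% | 82% | 86% | 92% |

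The before/after rate depends on the test and on the size of the shift. The concurrent comparison stays at 5% because both groups carry the same shift, which random allocation supports but concurrency alone does not.

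**The case against.** The strongest reply is that one-way ANOVA is normally a between-group test, so the authors may intend a control they did not describe. This has some weight. A reader might infer that the trial is single-arm and that its data cannot show effectiveness at all, but the documents do not go that far: they never say single-arm, and if groups exist the question may be answerable. The reply does not remove the fault, because no factor is named and baseline against week 8 is an equally available reading. The same section also mentions data sequencing, which matches nothing else in the plan, so its wording is a weak guide to the design.

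A second reply is that blood pressure is measured twice and some participants may enter without hypertension. A reader might infer that new hypertension cannot be assessed. That is too strong: it could be derived from the two readings. The fault is that it is unplanned. For cardiovascular illness the gap is complete.

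A third reply is that the illustration proves little. Its inputs are assumed, the 43% comes from a test the plan does not name, and the named ANOVA, read across visits, gives only 0.4% to 7% at the smaller shift. This is fair. The rates show how such a design behaves, and the conclusion does not depend on them.

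**Conclusion.** The objective is wrong as written and should be changed before results are reported.

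- **Prevention:** unsupported whether or not there is a control. This follows from the described participants and outcomes and needs no assumption.
- **Effectiveness:** the comparison is undefined. On the single-arm reading, which the text best supports, an 8-week change cannot be attributed to PSP. If there are groups, the plan does not let a reader tell whether they could support the claim.

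The size is qualitative: it decides what the trial may conclude. A reader might also infer that a randomised control is required. It is not; an uncontrolled study of marker change is legitimate if it is described as one.

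**What to change.** 1. State whether there is more than one group. If so, define the groups, the allocation and the ANOVA factor, and compare the groups on week-8 values adjusted for baseline.
2. In either case, remove prevention and cardiovascular illness from the objective and align it with the title: 8-week change in markers of metabolic syndrome. Blood pressure, total cholesterol and triglycerides qualify now. FBG, HbA1c, weight, skin fold thickness and obesity qualify only where a week-8 measurement is scheduled.
3. If the study is single-arm, also remove effectiveness and call it an exploratory uncontrolled before-after study. Replace one-way ANOVA with a paired analysis of change with confidence intervals. State that change is not attributed to PSP and that regression to the mean is a limitation.

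For a single-arm study the cost is wording plus one changed analysis sentence, and the downside is a weaker stated claim. A randomised control is optional, needed only to keep an effectiveness claim, and would be a redesign. With the same 50 people at 25 per arm, 80% power and two-sided 0.05, the detectable difference is 0.809 SD unadjusted. Adjusting for baseline multiplies this by √(1−ρ²): 0.809 × √(1−0.49) = 0.58 SD at an assumed ρ of 0.7 (0.65 at 0.6, 0.35 at 0.9).

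### The stated fill of 5 g of ground seed is not achievable in a swallowed capsule under generous assumptions, and without capsules per intake or grams per day the dose under test is unclear

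*Combined protocol and SAP*

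**What the plan says.** Three places in the combined protocol and SAP bear on the dose.

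- **Supplement preparation.** The seeds are dried and then ground: "Later, a mechanical grinder will be used to powder the dried seeds". No extraction, concentration or compaction is described. The fill is then given: "PS powder (PSP) will be packed in a capsule form, 5 g in each".
- **Span of study.** The 50 patients are treated "for the duration of 8 weeks with the supplementation of PSP capsule, twice a day". The capsule is mentioned without a number, and no daily dose in grams is given.
- **Objective.** The aim is stated as "To evaluate the effectiveness of pomegranate seed powder supplementation in preventing metabolic dysfunction", so the supplementation is the thing being evaluated.

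The 5 g fill is the only dose figure in the documents. They do not give a capsule size, a shell type, a powder density, a number of capsules per intake, or an alternative form such as a sachet. The Statistical Analysis Plan does not mention dosing.

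**The concern.** Five grams is a large mass for a capsule that is swallowed whole, and the material is plain ground seed rather than a concentrate. If the fill cannot be 5 g, the only sentence that fixes the dose cannot be followed as written. Whoever fills the capsules must then choose between fewer grams and more capsules, and the text does not say which.

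What is at stake is how the result is labelled. If the 5 g figure is carried into the report unchanged, an effect, or the lack of one, may be attributed to 10 g/day when another dose was taken. A reader could not repeat the regimen. A smaller dose would still be a valid test of that dose, provided that it is reported as such.

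**Working it through.** **Inputs from the documents:** 5 g per capsule (Supplement preparation); two intakes a day for 8 weeks, which is 56 days (Span of study); dried, mechanically ground seed (Supplement preparation).

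**Assumptions, not in the documents:** ordinary swallowed capsule, 0.68 to 1.4 mL; bulk density of ground seed, 0.4 to 1.0 g/mL. As a bound generous to the plan: a 2 mL capsule and nearly voidless powder at 1.4 to 1.5 g/mL.

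**Step 1. Dose implied by the text, with one capsule per intake.** 2 × 5 g = 10 g/day, and 56 × 10 g = 560 g per patient. The documents state no daily dose against which to check this, and no basis from which the 5 g could be reproduced.

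**Step 2. What a capsule holds.** Fill = volume × density.

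| Case | Volume (mL) | Density (g/mL) | Fill (g) |
|---|---|---|---|
| Ordinary, low | 0.68 | 0.4 | 0.27 |
| Ordinary, high | 1.4 | 1.0 | 1.4 |
| Generous bound | 2.0 | 1.4 | 2.8 |
| Generous bound, denser | 2.0 | 1.5 | 3.0 |

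**Step 3. The same check in reverse.**

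- Density needed to hold 5 g: 5 / 1.4 = 3.6 g/mL in a 1.4 mL capsule, and 5 / 2.0 = 2.5 g/mL in a 2 mL capsule. Both exceed the assumed upper limit of 1.5 g/mL.
- Volume needed for 5 g: 5 / 0.4 = 12.5 mL; 5 / 1.0 = 5.0 mL; 5 / 1.5 = 3.3 mL. The smallest of these is still above 2 mL.

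No combination in the ranges reaches 5 g.

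**Step 4. Doses compatible with the text once the 5 g fill is set aside.**

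- *A slip for 0.5 g.* 2 × 0.5 = 1 g/day with one capsule per intake. The density needed is 0.5 / 1.4 = 0.36 g/mL in a 1.4 mL capsule, so it fits there across the whole assumed range. In a 0.68 mL capsule it needs 0.5 / 0.68 = 0.74 g/mL, so it fits only in the upper part of the range.
- *One capsule per intake with whatever it holds.* From 2 × 0.27 = 0.54 g/day to 2 × 1.4 = 2.8 g/day for an ordinary capsule. The generous bound gives 2 × 2.8 = 5.6 to 2 × 3.0 = 6.0 g/day. This range includes the 1 g/day above.
- *5 g per intake over several capsules.* The dose is 10 g/day. The count per intake is 5 / 1.4 = 3.6, so at least 4 ordinary capsules. It is 5 / 0.5 = 10 capsules at 0.5 g each. At the generous bound, 5 / 2.8 = 1.8 and 5 / 3.0 = 1.7, so 2 in either case.

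**The case against.** The strongest reply is that the decisive step lies outside the documents. They do not state capsule volume, shell type, powder density or how the capsule is taken, so this is not an internal contradiction. That is correct, and it is why the finding is conditional. But the conclusion does not turn on a narrow choice: even the generous bound stops at 3.0 g. If a larger container, opened before use, is what is meant, 5 g could fit, and the text would need to say so.

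A second reply is that the number of capsules per intake is nowhere stated. One capsule is inferred from "with the supplementation of PSP capsule, twice a day", which carries no number. This stands, and it limits the finding. A reader might infer that patients will be under-dosed, or that the trial cannot deliver 10 g/day. The documents do not support that. Several capsules per intake could deliver 10 g/day in full, and then only the statement of 5 g per capsule would be wrong. Nor do they show that 0.5 g was intended; that is one possibility among several.

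A third reply is that staff will notice when they fill the first capsules. They may well do so. The text still gives them no rule for what to change, and nothing in it requires the change to be recorded.

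Finally, no comparison, outcome or analysis depends on this figure. That also stands. The defect is in how the intervention is defined, not in the inference.

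**Conclusion.** The point holds in a limited form. For a swallowed capsule of 0.68 to 1.4 mL and ground seed at 0.4 to 1.0 g/mL, the fill is about 0.3 to 1.4 g. At 2 mL and 1.4 to 1.5 g/mL it is about 2.8 to 3.0 g. A fill of 5 g is therefore not achievable in a swallowed capsule under any of these assumptions, and the dose sentence cannot be followed as written.

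The size of any departure from 10 g/day cannot be determined. The real dose may be about 1 g/day, another lower figure, or the full 10 g/day over several capsules. The 1 and 10 g/day readings differ tenfold, and nothing in the documents chooses between them. Any percentage shortfall would depend on both an assumed capsule and an assumed count, so none is claimed. The correction is worth making before dosing because the 5 g fill is the only figure that defines the intervention. No alpha, power or sample-size figure changes. Confidence is medium, since capsule volume and density are assumptions.

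**What to change.** - Before dosing, weigh a sample of filled capsules from the batch and replace the 5 g figure in Supplement preparation with the measured fill.
- In Span of study, state the number of capsules per intake and the grams per day.
- If 5 g per intake is intended, give the capsule count that delivers it, or use a sachet.
- Report the results against the grams per day actually given.

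Which mass to use is for the sponsor to say. The cost is weighing a few capsules and correcting two sentences, with no extra patients, visits or staff. The small downside is that the stated daily dose may fall, or that patients may have to take more capsules at each intake.

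### Fasting glucose and HbA1c are scheduled at baseline with no week-8 measurement stated, so the plan as written yields no glycaemic change data

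*Combined protocol and SAP*

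**What the plan says.** Outcome Evaluation sets out timing in two adjacent sentences. The first covers blood pressure, total cholesterol and TG, and ends "triglycerides (TG) will be measured at the enrollment point (i.e., baseline) and at the end of the 8-week intervention period". The second reads "Fasting blood glucose (FBG), glycated haemoglobin (HbA1c), and triglycerides (TG) will be measured at the enrollment point (i.e., baseline", and it stops there.

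The sentence after that is "A fresh blood sample from a vein will then be taken and examined". It carries no date and names no analyte. A list follows, introduced by "Detail of all data collected is as follows". It has eight items: weight, height, skinfold thickness, blood pressure, FBG, total cholesterol, TG and obesity. HbA1c is not among them, and the list gives no times.

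Participants names the qualifying impairments as "Insulin resistance, obesity, disturbed glucose level, hyper-cholesterol, hypertension and higher blood pressure". Span of study fixes the size and length: "The clinical trial on the 50 patients of metabolic syndrome will be conducted for the duration of 8 weeks". The Statistical Analysis Plan specifies one-way ANOVA at the 0.05 level and names neither an outcome nor a time point.

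**The concern.** An effect over eight weeks needs a value at the end of the eight weeks. The plan states one for blood pressure and the two lipids but not for either glycaemic marker, although the trial is titled for its effect on markers of metabolic syndrome and disturbed glucose is one of the ways to qualify. A site working from this text would have no instruction to run FBG or HbA1c at the final visit. A fasting value missed at week 8 cannot be obtained afterwards, so correcting the analysis later would not repair the loss.

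The double mention of TG, with different timing each time, is a second sign that this paragraph was not reconciled before it was issued.

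**Working it through.** No formula applies and the plan gives no figure to reproduce. The check is to follow each measure through the document.

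| Measure | First timing sentence | Second timing sentence | On the data list | Week 8 stated |
|---|---|---|---|---|
| Blood pressure | baseline, week 8 | not named | yes | yes |
| Total cholesterol | baseline, week 8 | not named | yes | yes |
| TG | baseline, week 8 | baseline | yes | yes |
| FBG | not named | baseline | yes | no |
| HbA1c | not named | baseline | no | no |

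**Count.** Five measures are given a time. Three have a stated week-8 point and two do not (3 + 2 = 5). Of the eight listed items, three have both times, one (FBG) has baseline only, and four (weight, height, skinfold thickness, obesity) have none (3 + 1 + 4 = 8).

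**Does the venous-sample sentence fill the gap?** Its word *then* could point to a follow-up draw, but the sentence reads equally well as the baseline draw. With no date and no analyte, nobody could schedule a week-8 FBG from it.

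**Does the analysis plan fill the gap?** No. It refers to host parameter data in general and gives no times.

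**Which explanations remain?**

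1. A week-8 clause was dropped by mistake. The repetition of TG suggests careless drafting and fits this.
2. The baseline tests serve eligibility or description. HbA1c's absence from the data list fits this. FBG's place on that list, under Outcome Evaluation, speaks against it for FBG, though not conclusively.
3. Glycaemic follow-up was not planned.

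The document does not decide among them.

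**Size, assuming all 50 participants attend.** Baseline has four blood measures: 4 × 50 = 200 results. Week 8 depends on the reading:

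- as written (total cholesterol, TG): 2 × 50 = 100
- if FBG was intended: 3 × 50 = 150
- if HbA1c was intended as well: 4 × 50 = 200

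The difference from the literal reading is 150 − 100 = 50 FBG results, or 200 − 100 = 100 results for both markers.

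**The case against.** The strongest reply is that the plan may never have meant FBG as a follow-up outcome. The Objective gives hypertension and cardiovascular illness as its examples, neither of them glycaemic, and blood pressure does have week-8 data. Disturbed glucose is only one of six listed impairments, so a participant can qualify without it. Being on the data list does not prove repeat measurement, since height is on the same list. No primary outcome is named. On this view the proper request is only that the sponsor state which was meant.

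Part of this stands. FBG is a plausible outcome, not a declared one, and the loss of change data follows only if the text is applied literally. The TG wording also has no practical consequence: the second sentence does not say baseline only, so obeying both sentences gives the full TG schedule. A tally of entry impairments against week-8 measures would add little, because hypertension and higher blood pressure overlap.

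It does not remove the point. The Objective also speaks of metabolic dysfunction generally, which can include glucose. The missing week-8 time is a fact of the text on every reading. A week-8 FBG improves the trial whether it was left out by slip or by intention, because without it the plan cannot address one of the markers it lists.

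**Conclusion.** The concern holds. No week-8 measurement of FBG or HbA1c is stated anywhere: two of the five timed measures. On the literal reading, week-8 FBG is available for 0 of 50 participants; if a clause was dropped, 50 of 50 were intended. That range assumes full attendance.

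Confidence is high that the time point is unstated and that the two TG sentences are inconsistent. It does not extend to what the sponsor intended, and the loss of glycaemic change data is conditional on staff following the words as they stand. Blood pressure, total cholesterol and TG are unaffected. This should be fixed before the first week-8 visit.

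**What to change.** Replace the two timing sentences with one: blood pressure, total cholesterol, TG and FBG are measured at baseline and at the end of week 8, with FBG run on a fasting venous sample from the draw at each time. Give the venous-sample sentence its date and analytes, or fold it into the new one. For HbA1c, either measure it at both times and add it to the data list, or declare it a baseline descriptor. In the same edit, the sponsor should state the time points for weight, height, skinfold thickness and obesity; the document does not show which were intended.

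**Cost.** The wording change is trivial. Extra FBG assays number 0 if week 8 was already intended and otherwise up to 50; with HbA1c, up to 100 assays in total. Participants must fast for the week-8 visit if that was not already planned. Week-8 total cholesterol and TG imply a blood draw, so on that inference no extra visit or draw is needed. Each untimed item the sponsor chooses to repeat adds up to 50 assessments at the same visit.

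The document does not show whether week-8 visits have begun. If they have, the sponsor should record which measures were actually taken at which times.

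### The only named test, one-way ANOVA, has no stated comparison; applied to baseline versus week 8 in the same people, it ignores pairing and can miss real changes

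*Combined protocol and SAP*

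**What the plan says.** The Statistical Analysis Plan has one sentence on testing: "Using one-way ANOVA, the statistical significance of the host parameter data will be determined". The threshold follows: "When the p-values are less than 0.05, differences are considered significant". No factor, group, time point or outcome is attached to the ANOVA, and the host parameters are not defined. R is mentioned for data sequencing without a test, and the rest is descriptive summary. No paired test, repeated-measures ANOVA or mixed model appears.

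On design, Type of Study says only "This trial is prospective clinical type". Span of study says "The clinical trial on the 50 patients of metabolic syndrome will be conducted for the duration of 8 weeks"; the same sentence names the supplement as the only treatment. No control, randomisation or second arm is described. Single-arm is therefore an inference, but nothing in the text points the other way.

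On timing, Outcome Evaluation says "Blood pressure, total cholesterol, and triglycerides (TG) will be measured at the enrollment point (i.e., baseline) and at the end" (that is, at week 8). The next sentence places fasting glucose and HbA1c at baseline only. It lists triglycerides again, also at baseline only, which looks like a drafting slip. No times are given for weight or skinfold thickness.

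**The concern.** Baseline versus week 8 in the same people is the only comparison the text supports. Ordinary one-way ANOVA assumes independent observations. With two time points it is the pooled two-sample t-test squared, so stable differences between people enter the error term when they should cancel.

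With positive within-person correlation the test becomes conservative: its true type I error falls below the stated 5%, and power is lost. The harm is missed effects, not false positives. This is the trial's only named inferential method, so a null result could reflect the test and not the supplement. An analyst who followed the sentence literally would run the wrong analysis; one who read it as repeated-measures ANOVA would run a suitable one. The plan does not settle which.

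**Working it through.** The plan states no power, effect size, SD or sample-size derivation, so there is no figure of its own to reproduce. The check below sizes the effect of ignoring pairing.

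**Inputs from the documents:** n = 50 (Span of study); two time points (Outcome Evaluation); significance at p < 0.05 (Statistical Analysis Plan), taken as two-sided.

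**Assumptions not in the documents:** 50 complete pairs, normal data, equal SDs at both times, within-person correlation ρ of 0.3, 0.5, 0.7 or 0.8, and true changes of 0.3 to 0.6 SD.

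**Standard error of the mean change, in SD units**
- One-way ANOVA uses √(2/n) = √(2/50) = 0.200, whatever ρ is.
- The correct value is √(2(1−ρ)/n). At ρ = 0.5 this is √(1/50) = 0.141.
- The ratio is 1/√(1−ρ). At ρ = 0.5 this is 1.41.

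**Observed change needed for p < 0.05**
- ANOVA (1 and 98 df): 1.984 × 0.200 = 0.397 SD at any ρ.
- Paired t (49 df): 2.010 × √(2(1−ρ)/50). At ρ = 0.5 this is 2.010 × 0.1414 = 0.284 SD.

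**True type I error of the ANOVA.** The large-sample form is 2(1 − Φ(1.96/√(1−ρ))), which gives 1.9% at ρ = 0.3. The table shows the simulated values.

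**Power.** ANOVA by simulation; paired test from the noncentral t. Simulation error and rounding amount to about half a percentage point.

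| | ρ = 0.3 | ρ = 0.5 | ρ = 0.7 | ρ = 0.8 |
|---|---|---|---|---|
| ANOVA SE / correct SE | 1.20 | 1.41 | 1.83 | 2.24 |
| ANOVA true type I error | 2.0% | 0.7% | 0.06% | <0.01% |
| Observed change needed, ANOVA / paired (SD) | 0.397 / 0.336 | 0.397 / 0.284 | 0.397 / 0.220 | 0.397 / 0.180 |
| Power at 0.3 SD, ANOVA / paired | 29 / 42% | 25 / 55% | 20 / 77% | 16 / 91% |
| Power at 0.4 SD | 51 / 65% | 51 / 79% | 52 / 95% | 52 / 99% |
| Power at 0.5 SD | 73 / 83% | 76 / 93% | 82 / 99% | 86 / >99% |
| Power at 0.6 SD | 88 / 94% | 92 / 99% | 96 / >99% | 98 / >99% |
| Change detectable with 80% power (SD) | 0.54 / 0.48 | 0.52 / 0.40 | 0.49 / 0.31 | 0.48 / 0.26 |

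**Boundary checks.** At ρ = 0 the two tests agree (type I error about 5% for both). Only negative correlation reverses the direction: at ρ = −0.2 the ANOVA's type I error is about 7.4%.

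**Repeated-measures reading.** With two time points, one-way repeated-measures ANOVA gives F equal to the squared paired t. On a simulated data set both were 3.392 with p = 0.0716. If that is what was meant, the fault disappears, but the plan has to say so.

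**The case against.** The strongest reply is that the proven defect is under-specification and not a wrong test. The pairing fault arises only if the independent-groups ANOVA is applied to the two time points. Repeated-measures ANOVA is neither stated nor excluded, and an undescribed comparator would make a between-arm ANOVA free of this fault. That stands as a caution, and the conclusion is conditional for that reason. It does not rescue the sentence: no second arm appears in the text, and under every reading the comparison must still be named.

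The size is also entirely assumed. The loss depends on correlation as much as on effect: at 0.3 SD it runs from 13 percentage points (ρ = 0.3) to 75 (ρ = 0.8). That is right, and it is why a range is shown. Nothing in the documents places the trial where the loss is small.

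Finally, the error is conservative, and the larger threat to validity is the absence of a described control in people enrolled for abnormal values. This also stands. If a 0.3 SD change were wholly regression to the mean, the paired test would call it significant 42% to 91% of the time, against 29% to 16% for the ANOVA. That limits what any before–after test can show. It does not justify a wrong standard error as a safeguard.

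**Conclusion.** The concern holds and should be corrected before analysis. The only named test has no stated comparison, and in its ordinary form it does not fit the one comparison the text supports.

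With positive within-person correlation, the usual case for repeated readings in one person, the loss of power is:
- 13 to 75 percentage points for a 0.3 SD change;
- 14 to 47 points for 0.4 SD;
- 10 to 17 points for 0.5 SD;
- 7 points or fewer for 0.6 SD.

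These figures rest on the assumed correlations of 0.3 to 0.8, equal SDs and 50 complete pairs. The conclusion also rests on the inference that the trial is single-arm and on the ordinary reading of one-way ANOVA. It applies directly to blood pressure, total cholesterol and triglycerides. For fasting glucose, HbA1c, weight and skinfold thickness, the schedule as written supports no within-person test.

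**What to change.** Replace the ANOVA sentence with wording such as:

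> For each continuous marker recorded at both baseline and week 8, the within-participant change will be tested with a paired t-test in participants who have both values, and reported as mean change with 95% CI. (With two time points, one-way repeated-measures ANOVA is identical.)

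Optionally, add a mixed model with time as a fixed effect and participant as a random effect as a sensitivity analysis. It retains the baseline values of participants without a week-8 reading. If a control group does exist, describe it and compare groups at week 8 by ANCOVA adjusted for baseline.

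In Outcome Evaluation, reconcile the two timing sentences, including the double listing of triglycerides. Make clear whether fasting glucose and HbA1c are repeated at week 8, and give the times for weight and skinfold thickness. The paired analysis covers those markers only once this is done.

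For blood pressure, total cholesterol and triglycerides the cost is SAP wording only, with the same data and the same software (SPSS or R). The other markers also need the schedule text settled. The report should state that a paired test cannot separate a supplement effect from regression to the mean or time trends, and does not remove bias if dropout is related to change.
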